2 STUDY DESIGN

2.1 Study Type

The RAMOSA Trial is a multi-center, prospective, controlled trial. Sub-studies are not permitted without the prior approval of Sponsor.

2.2 Scale

The study will be conducted at a maximum of 3 centers in which at least one study center will be in the United States. Patients will be enrolled to provide data from up to 48 subjects. Data from 43 subjects is required to demonstrate efficacy and we count 10% for dropouts (Section 3.2 Sample Size Rational). When the treatment limit of 48 subjects is reached, Sponsor may opt to submit for expanded access.

2.3 Duration

The duration of the RAMOSA trial is expected to be approximately 24 weeks, and follow-up data will continue to be collected for 6 months post-treatment. Enrollment in the RAMOSA trial is anticipated to require approximately 1 year from the first regulatory authority approval. Once 48 subjects have been followed for 24 weeks, the clinical data will be reported to regulatory authorities. All subjects enrolled in this study must be followed according to the investigational plan unless Sponsor notifies the Investigator to the contrary, or Sponsor has officially closed the study.

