	
 • examination • ASA class III ,IV, V • Latex allergy • Lidocaine allergy • Pregnancy or plans to become pregnant 
Note: women of childbearing potential must demonstrate a negative pregnancy test upon enrollment; those patients qualified to progress to RFA must also demonstrate a negative pregnancy test within 7 days prior to the date of RFA procedure.
 
 • Major depression or non-stabilized psychiatric disorder • Drug or alcohol abuse • Previous palatal or tongue surgery • Stable or unstable angina • CHF • Moderate or severe valvular disease • TIA/CVA • Carotid stenosis or endarterectomy • Anemia • Room air SpO₂ < 95% • Pulmonary hypertension • Dialysis • Central or mixed apnea ≥ 10% of respiratory events • Participation in another clinical study (enrolled in any concurrent study) whose investigational plan is judged to interfere or affect any of the measures of this study
Study Endpoints	Effectiveness of the CelonProSleep plus will be assessed by demonstrating adequate reduction in AHI and ODI as defined below: A responder to the CelonProSleep plus RFA treatment is defined as a patient with an AHI reduction ≥50% and a reduction of their ODI ≥25% at the 6-month follow-up PSG, and their AHI at the 6-month follow-up is <20.
# of patients	43 + 10% dropouts (n=48)
Treatment Procedure	Three treatment sessions of RF ablation of the soft palate (7 lesions) and the base of tongue (6 lesions).
Statistical Analysis of Endpoints	The performance endpoints will be assessed by recording the functional parameters and by monitoring the patient clinical status. Safety assessments will consist of recording of any adverse events. Variables will be analyzed by using appropriate statistical techniques for parametric and continuous measurements.
Follow-up	6 months after the last RFA treatment.
Study Duration	24 weeks plus 6 months of follow-up for each patient

Table of Contents

1. BACKGROUND.....	9
1.1 Obstructive Sleep Apnea.....	9
1.2 Diagnosis of Obstructive Sleep Apnea.....	9
1.3 Surgical Therapy for OSA.....	10
1.4 CelonProSleep plus	11
1.5 Safety of RF ablation of the soft palate and base of tongue.....	12
2. STUDY DESIGN.....	17
2.1 Study Type.....	17
2.2 Scale.....	17
2.3 Duration.....	17
2.4 Study objectives.....	17
2.5 Determination of last Follow-up visit.....	18
3. HYPOTHESES AND DATA ANALYSIS.....	19
3.1 Primary Efficacy Endpoints.....	19

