Considering these data the current study will have a follow-up period of 6 months after the last RFA treatment. The period of six months is chosen because 1) this is sufficient time for healing of the treated sites of the upper airways and, 2) it is enough time for following fortification or decline of therapeutic effects, 3) it is not so long that the strength of association of treatment and effect is lost, and 4) it allows the possibility for longer term follow-up data on those patients who can be relied on for a longer follow-up. In addition, a six month follow-up time will allow for earlier identification of non-responders so that these patients can be referred for additional therapy as indicated.

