3 HYPOTHESES AND DATA ANALYSIS

3.1 Primary Efficacy Endpoints

The primary effectiveness of the study is to demonstrate a clinically significant reduction of OSAS from Baseline PSG sleep study to the 6-month follow-up PSG in adults (≥ 22 years) with obstructive sleep apnea (AHI 10-30) and BMI ≤ 32 .

Effectiveness of the CelonProSleep *plus* will be assessed by demonstrating adequate reduction in AHI and ODI as defined below:

A responder to the CelonProSleep *plus* RFA treatment is defined as a patient with an AHI reduction $\geq 50\%$ **and** a reduction of their ODI $\geq 25\%$ at the 6-month follow-up PSG, and their AHI at the 6-month follow-up is < 20 .

The aim of the study is to show that at least 50% of participants met the primary endpoint above. This will be tested with one sided 97.5% confidence interval with $\pm 20\%$ margin of error^{73, 74}.

In order to record and analyze data for determining the primary endpoints, patients will undergo a PSG sleep study to establish a mean baseline AHI and ODI. Patients will then be treated with a series of three treatments of upper airway radiofrequency ablation with the bipolar electrosurgical electrode CelonProSleep *plus* (Olympus Winter & Ibe, Germany) over 18 weeks. The patient will undergo a second PSG sleep study at the final follow-up examination 6-months later. Mean changes in AHI will be compared for each individual and among all patients. Surgical success is defined if at least 50% of participants experience at least 50% reduction in AHI and 25% reduction in ODI (Performance Goal, PG=50%).

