6 DURATION

This study has a minimum of eight visits. The first visit, the Screening Visit, is planned for determining whether patient qualifies for the study. This visit will take up to 1 hour. In the second visit, the Baseline Visit, which occurs up to 2 weeks later, standard medical history, demographics and various questionnaires will be obtained from the patient. In addition, the patient will undergo a Müller's Maneuver and will be sent to the sleep lab for a PSG study (one night). This visit will last about 60 minutes.

The third visit is the first RF treatment session and will last about 1 hour. The fourth and fifth visits involve additional RF treatments and will last about one hour each. The first follow-up visit will occur 6 weeks after the third treatment visit and will last as well about 1 hour. The 7th visit, the 6-month follow-up visit, will occur 6 months later and will be no more than 1 hour. At the end of this visit the patient will be admitted to a sleep labor for undergoing the 2nd PSG study. Finally, the 8th and final Visit will last about 30 minutes. The patients may require additional visits in case of complications that are needed to be treated in the hospital or if they have a question or concern. The entire duration of the study for an individual patient is no longer than 24 weeks plus 6 months of follow-up.

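### Section 2.3 triggers regulatory reporting at 24 weeks of follow-up, which as written falls before the 6-month PSG that carries the primary endpoint

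*Combined protocol and SAP*

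**What the plan says.** Section 2.3 (Duration) sets the trigger: "Once 48 subjects have been followed for 24 weeks, the clinical data will be reported to regulatory authorities". The same paragraph describes the trial as "expected to be approximately 24 weeks, and follow-up data will continue to be collected for 6 months post-treatment", so the 24 weeks and the 6 months are separate periods. Two other places make the same split. The synopsis gives the study duration as "24 weeks plus 6 months of follow-up for each patient", and Section 6 says "The entire duration of the study for an individual patient is no longer than 24 weeks plus 6 months of follow-up".

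Appendix I places Visit 6 at up to week 24 and marks no PSG and no ODI there. Section 6 fixes that visit relative to treatment: "The first follow-up visit will occur 6 weeks after the third treatment visit". Section 5.6 lists ESS, FOSQ, VAS scales and a physical examination for it.

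The primary endpoint in Section 3.1 concerns a "clinically significant reduction of OSAS from Baseline PSG sleep study to the 6-month follow-up PSG". Section 2.5 anchors the period: "the current study will have a follow-up period of 6 months after the last RFA treatment". Section 6 lists the 6-month visit directly after Visit 6 and can be read as counting from there. Section 5.7 allows the second PSG up to 30 days later, and Appendix I allows 4 weeks.

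No other section sets a later reporting trigger or says that the report waits for the 6-month PSG.

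**The concern.** A report to regulators would be expected to contain the endpoint the study was sized for. Here the condition for reporting uses a time point at which a subject has had no post-treatment PSG. Early enrollees would have passed their 6-month PSG by the time the last subject reaches week 24, but late enrollees would not.

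The plan has no rule for subjects whose PSG is still pending. Section 3.1.2 and the full analysis set in Section 8.4 require the 6-month assessment or all eight visits. The non-responder rules in Section 3.1.1 and the missing-data rule in Section 8.5 deal with subjects who die, fail treatment, leave or are lost. How pending subjects are counted in such a report would be decided ad hoc.

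There is also a counting problem. The trigger needs 48 subjects followed, but 48 is the number enrolled after allowing for dropout.

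**Working it through.** **Inputs.** Third ablation (Visit 5) at up to week 18 and Visit 6 at up to week 24 (Appendix I); second PSG up to 30 days after the 6-month visit (Section 5.7); enrolment about 1 year (Section 2.3); 43 subjects required, 48 with 10% dropout (Sections 2.2 and 3.2). I take 6 months as 26.1 weeks and 30 days as 4.3 weeks.

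**The plan's own figure.** 43 / 0.9 = 47.8, rounded up to 48, as stated. The expected number of completers is 48 × 0.9 = 43.2. If each subject independently had a 10% chance of leaving, the chance that all 48 stay would be 0.9^48 = 0.006.

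**When the primary PSG falls.** Gap = PSG week − 24. Subjects without a PSG when the 48th reaches week 24 = 48 × gap / accrual period, with even accrual over 52 weeks and all 48 retained (computed from unrounded weeks):

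| 6 months run from | PSG window | PSG week | Gap (weeks) | 48 × gap / 52 |
|---|---|---|---|---|
| Last ablation | none | 18 + 26.1 = 44.1 | 20.1 | 18.5 |
| Last ablation | 30 days | 44.1 + 4.3 = 48.4 | 24.4 | 22.5 |
| Visit 6 | none | 24 + 26.1 = 50.1 | 26.1 | 24.1 |
| Visit 6 | 30 days | 50.1 + 4.3 = 54.4 | 30.4 | 28.0 |

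Counting 48 evenly spaced subjects one by one gives 19, 23, 24 and 28. So about 18 to 28 would lack the primary outcome, and about 20 to 30 would have it, against the 43 required.

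The weeks in Appendix I are upper limits, but the gap from Visit 6 does not depend on them. Visit 6 is 6 weeks after the third ablation and the PSG is 26.1 weeks after it, so the gap is at least 26.1 − 6 = 20.1 weeks.

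**Sensitivity to accrual** (one-by-one counts, smallest to largest gap):

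| Accrual period | Subjects without primary PSG |
|---|---|
| 26 weeks | 37 to 48 |
| 52 weeks | 19 to 28 |
| 78 weeks | 13 to 19 |
| 104 weeks | 10 to 14 |

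**Alternative reading: 24 weeks since the last treatment.** The trigger point is 18 + 24 = week 42. With 52-week accrual the number lacking a PSG is 2 (PSG at week 44.1), 6 (48.4), 8 (50.1) or 12 (54.4). The trigger is still early, but by much less.

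**The case against.** The strongest reply is that Section 2.3 does not call this report the primary or final analysis. Sections 3.1.2, 8.1 and 8.4 tie the primary analysis to 6-month data, and a subject who has only reached Visit 6 is in neither the primary analysis population nor the full analysis set. The next sentence of Section 2.3 keeps all subjects under follow-up unless the sponsor says otherwise. This stands. A reader might infer that the primary test would be run early, but the documents do not say so.

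A reader might also infer an extra, unplanned look that inflates the type I error. That is not supported either. The report is written into the plan, no test, decision or stopping boundary is attached to it, and the formal interim analyses are described separately in Section 8.6.

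Nor would the report rest mainly on 6-week symptom scores. With one-year accrual, 20 to 30 subjects would already have their 6-month PSG.

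The 24 weeks may be a loose rendering of 6 months after treatment; the protocol equates 30 days with 4 weeks for the PSG window. This is possible but weaker, because the same paragraph sets 24 weeks apart from the 6-month follow-up. Even so, the trigger would precede the PSG for about 2 to 12 subjects.

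Section 1.2 mentions a WatchPAT home study at both follow-up visits, which would give some AHI estimate at Visit 6. Section 5.6 and Appendix I do not schedule it, and the primary endpoint is defined on PSG, so it does not fill the gap.

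Finally, Section 2.2 speaks of up to 48 subjects and requires 43, so a sensible reader would not wait for dropouts. That makes the counting problem minor, but the trigger as worded still does not say so.

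**Conclusion.** The concern holds as a premature and loosely worded reporting trigger. By the protocol's own use of the term, 24 weeks ends at Visit 6, at least 20 weeks before the primary PSG and up to about 30 weeks before it, depending on the anchor and the PSG window.

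The size depends on accrual, which the protocol gives only as about one year; even accrual is an assumption. On that basis about 18 to 28 of 48 subjects would lack the primary outcome at the trigger. Accrual over 104 to 26 weeks moves this to roughly 10 to 48, and the weaker reading of 24 weeks reduces it to about 2 to 12 with one-year accrual. These counts ignore dropout.

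The finding goes no further than the timing and completeness of the report. It does not show an early primary analysis or any loss of error control.

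**What to change.** Replace the trigger sentence in Section 2.3 with: *once every treated subject has completed the 6-month post-treatment PSG or has exited the study, the clinical data will be reported*. This aligns the report with the primary endpoint, and the exit clause removes the need for all 48 to be followed. It works whichever anchor applies, but Sections 2.5 and 6 should also be reconciled on where the 6 months start.

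If an earlier report is wanted, it should be named separately, with its content stated and a note that it is not the primary analysis.

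The cost is one sentence and a later report: about 20 to 30 weeks after the literal trigger.

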2.4 Rational for patient selection

This study aims to evaluate the CelonProSleep *plus* for multi-level radiofrequency ablation (RFA) of the palate and base of tongue as a treatment for mild to moderate obstructive sleep apnea syndrome (OSAS) in patients with AHI of 10-30 and BMI ≤ 32 . The AHI cut-off of 30 is used because patients with AHI > 30 have OSA of such severity that they are unlikely to respond to RFA. Unlike traditional sleep surgery, RFA does not involve radical removal of tissue but works primarily by remodeling and stiffening the tissues of the upper aerodigestive tract. A meta-analysis of RFA studies found a mean AHI reduction of 45% after 24-month follow-up³⁵. Since standard measures of surgical success (AHI reduced by 50%) are applied in this study, we anticipate that many patients with severe (AHI > 30)

apnea would not be considered a surgical success and should therefore be excluded in favor of other more effective therapy for severe OSA (CPAP or traditional surgery). RFA demonstrates improved sleep outcomes if the procedure is repeated on several occasions in order to deliver enough energy to create the critical mass of scar tissue to offset the increased collapsibility of the upper airway^{32, 35}. Therefore, the present trial will repeat upper airway RFA on three occasions in order to maximize treatment effect. The treatment sessions are separated by six weeks since it takes approximately 3-4 weeks for the lesion to convert to scar and therefore all tissues should be healed by week 6³⁶. In addition, multiple studies have found that rates of surgical success for OSA decline with increasing patient BMI. This is especially true for patients with morbid obesity (BMI >40) who have a significant level of lingual and parapharyngeal fat which increase the collapsibility of the upper airway. Since most patients with OSA are overweight to obese, too low of a BMI cutoff may be overly restrictive³⁷. The BMI cut-off of 32 is a convenient rule-of-thumb frequently used by sleep surgeons which captures a large percentage of the OSA population which are more likely to succeed with sleep surgery while excluding the most obese subset who are less likely to succeed and are at increased risk for surgical complications.

2.5 Determination of last Follow-up visit

Although in-laboratory PSG is the gold standard for diagnosing OSAS, there are a few factors that may lead to biased results when using PSG for determining treatment success in studies that apply long-term follow-up measurements (e.g. one year). Some of these factors are 1) selecting only patients that are willing to participate in a PSG study might lead to a selection bias and thus, excluding patients who are suited for the tested treatment, but are not willing to participate in a PSG study; 2) a long-term follow-up may lead to a high number of dropouts because of various reasons as described below; and 3) PSG records biophysiological changes during sleep, but not the changes occurred in daily life situation from the last treatment till the follow-up visit (e.g. change in personal or professional status, weight changes, or other factors that are not related to the treatment, but contributing to sleep quality). Thus, a longer interval between the treatments to the final follow-up visit will result in an increase in missing data, weaken the association between treatment and effect, and potentially introduce bias into the study.

An analysis of the (prospective) RFA studies that are discussed in section 1.5 (Table 1), reveals correlative relations between the amount of dropouts and the interval between last RFA treatment and the follow-up visit. 12 of these studies had a follow-up visit of up to 4 months^{29, 31, 39, 46, 48, 50, 53-55, 58, 62, 67}. The mean dropout in these studies was 9,7%, in compared to 24,7% in studies with follow-up of up to 12 months (7 studies^{30, 47, 51, 56, 59, 68, 69}) and 24% in studies in which the follow-up was conducted within 24 months (2 studies^{34, 52}).

Out of the 22 reviewed studies only two studies reflect on the problem of keeping a study population for long-term follow-ups (e.g. 12 months,)). Steward et al. (2005)³⁴, aimed to conduct a long term follow-up with patients treated with RFA (one year, home sleep-study). To this end, all potentially eligible subjects from a parent trial were offered inclusion in the study. Twenty nine of 46 potentially eligible subjects agreed to participate (63%). Of those 17 potentially eligible subjects who did not participate (37%), 5 could not be located (moved or bad phone number), 4 refused, and 8 reported that they were too busy or missed scheduled appointments and didn't follow-up despite multiple phone

calls. In addition, three patients were excluded because of additional treatment after completion of RFA (2 CPAP, 1 surgery).

Discussing the limitations of their study, Friedman et al. (2007)⁵⁹ attribute one of the study' limitations to the large number of patients who are lost to follow-up, and declare "Unfortunately, many patients are not willing to return for a follow-up PSG". Based on an "intent-to-treat" analysis the cure rate was 37.2%. The authors estimate, however, that the "true" success rate is closer to 47.5% and state that, "it is possible that most of the patients who have had elimination of symptoms are those who are least likely to participate in the follow-up PSG". In order to increase participation in the long-term follow-up visit, patients were offered free adjunctive treatment such as additional Pillar implants and radiofrequency tongue base reduction based on need as determined by the postoperative PSG. Apparently, most patients who were willing to participate in the follow-up visit, were those who had persistent snoring or symptoms and wanted additional treatment⁵⁹.

The problem of a high number of dropouts in long-term follow-ups is not limited to RFA studies. Walker et al. (2007)⁷⁰, for example, conducted a study with an extended follow-up (15 months) that was based on an initial study with 90-days follow-up. Out of 53 patients that were enrolled to the initial study, 13 patients were either unable to be contacted or declined further participation; one site with seven patients from the initial study did not participate in the extended follow-up; seven patients did not meet the study inclusion criteria and four patients had other treatments for OSA (e.g., nasal CPAP, uvulopalatopharyngoplasty, laser-assisted uvulopalatoplasty) rendered during the extended follow-up period. Thus, the extended follow-up included only 22 patients (41.5%).

Doff et al (2013)⁷¹, conducted a randomized study that compared outcomes of oral appliances(Group I) and CPAP (Group II) after 2 years follow-up. Out of 51 patients in Group I and 52 patients in Group II that started the clinical trial, only 29 and 37 patients (respectively) finished the 2-years follow-up study (64%).

Considering these data the current study will have a follow-up period of 6 months after the last RFA treatment. The period of six months is chosen because 1) this is sufficient time for healing of the treated sites of the upper airways and, 2) it is enough time for following fortification or decline of therapeutic effects, 3) it is not so long that the strength of association of treatment and effect is lost, and 4) it allows the possibility for longer term follow-up data on those patients who can be relied on for a longer follow-up. In addition, a six month follow-up time will allow for earlier identification of non-responders so that these patients can be referred for additional therapy as indicated.

3 HYPOTHESES AND DATA ANALYSIS

3.1 Primary Efficacy Endpoints

The primary effectiveness of the study is to demonstrate a clinically significant reduction of OSAS from Baseline PSG sleep study to the 6-month follow-up PSG in adults (≥ 22 years) with obstructive sleep apnea (AHI 10-30) and BMI ≤ 32 .

Effectiveness of the CelonProSleep *plus* will be assessed by demonstrating adequate reduction in AHI and ODI as defined below:

A responder to the CelonProSleep *plus* RFA treatment is defined as a patient with an AHI reduction $\geq 50\%$ **and** a reduction of their ODI $\geq 25\%$ at the 6-month follow-up PSG, and their AHI at the 6-month follow-up is < 20 .

The aim of the study is to show that at least 50% of participants met the primary endpoint above. This will be tested with one sided 97.5% confidence interval with $\pm 20\%$ margin of error^{73, 74}.

In order to record and analyze data for determining the primary endpoints, patients will undergo a PSG sleep study to establish a mean baseline AHI and ODI. Patients will then be treated with a series of three treatments of upper airway radiofrequency ablation with the bipolar electrosurgical electrode CelonProSleep *plus* (Olympus Winter & Ibe, Germany) over 18 weeks. The patient will undergo a second PSG sleep study at the final follow-up examination 6-months later. Mean changes in AHI will be compared for each individual and among all patients. Surgical success is defined if at least 50% of participants experience at least 50% reduction in AHI and 25% reduction in ODI (Performance Goal, PG=50%).

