3.1.3 Hypotheses

Null Hypothesis. Multi-level radiofrequency ablation of the upper airway in adults (age ≥ 22 years) with obstructive sleep apnea (AHI 10-30; Lowest O₂ sat $\geq 80\%$) results in no improvement as defined by the composite endpoint, Section 3.1.

$$\begin{aligned} H_0: \text{TT RAMOSA} &\leq \text{PG} \\ H_A: \text{TT RAMOSA} &> \text{PG}, \end{aligned}$$

where TT_{RAMOSA} is the proportion of AHI and ODI responders to the multi-level radiofrequency treatment. For this objective, the PG is established at 50%.

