8.1 Primary Efficacy Endpoint

The primary endpoint of AHI and ODI obtained at the 6-month follow-up will be compared to the Baseline measurement. The subject is a responder if the reduction in AHI is $\geq 50\%$, and ODI reduction is $\geq 25\%$. The proportion of subjects meeting the responder criteria among all included subjects will be evaluated using a one-sided 95% confidence interval. In addition one sample test of the proportion of patients meeting the PG at 6month is significantly different than 50%. The study is designed to demonstrate success rate of 20% beyond the PG of 50%. Proportion with 95% CI will be given using normal approximation to the Binomial. P-Value will be derived based on the exact binomial distribution of the null hypothesis, that is assuming $p=0.5$.

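### Section 3.1 defines success as an observed responder share of 50% or more, while 3.1.3, 3.2 and 8.1 test against 50%: with 43 patients, 22 to 27 responders passes one rule and fails the other

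*Combined protocol and SAP*

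**What the plan says.** Section 3.1 (Primary Efficacy Endpoints) contains three statements about success:

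- the aim: "The aim of the study is to show that at least 50% of participants met the primary endpoint above";
- the means: "This will be tested with one sided 97.5% confidence interval with $\pm 20\%$ margin of error";
- a definition: "Surgical success is defined if at least 50% of participants experience at least 50% reduction in AHI and 25% reduction in ODI", followed by a parenthesis naming 50% as the performance goal (PG).

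Section 3.1.3 sets the hypotheses as proportion at or below PG against proportion above PG, and adds "For this objective, the PG is established at 50"%. In words, its null is that treatment "results in no improvement as defined by the composite endpoint, Section 3.1".

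Section 3.2 sizes a one-sample Z test: P0 = 0.50, P1 = 0.70, target alpha 0.025, reject if Z is at least 1.96, n = 43, power 0.8081, actual alpha 0.0330. Its text, however, places 50% in the alternative and attaches a line requiring P1 minus P0 to be at least 20%.

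Section 8.1 uses a one-sided 95% interval by normal approximation and an exact binomial p-value at p = 0.5. It describes a "one sample test of the proportion of patients meeting the PG at 6month is significantly different than 50"%, and says "The study is designed to demonstrate success rate of 20% beyond the PG of 50"%.

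**The concern.** The definition in 3.1 is met as soon as half the patients respond, whatever the uncertainty. The hypotheses are met only when the data exclude a true rate of 50% or less. These are different decisions, and no section says that the definition merely names the benchmark or that the test takes precedence.

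The study is single-arm and open-label, and its data go to regulators (2.3). A result such as 25 of 43 could be called a success under 3.1 and a failure under 3.1.3. Choosing between the rules after seeing the count would not be credible.

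The surrounding text does not help. The ±20% in 3.1 reads like a tolerance. The level is 97.5% in 3.1 and 95% in 8.1. The interval is a normal approximation while the p-value is exact.

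**Working it through.** **Inputs.** n = 43 (2.2, 3.2); p0 = 0.50 (3.1.3); p1 = 0.70, Z using the standard error under p0, critical value 1.96 (3.2); one-sided 97.5% interval (3.1); one-sided 95% normal-approximation interval and exact p-value (8.1).

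**1. The plan's own figure.** Z = (r/43 − 0.5)/√(0.25/43).

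- r = 27: (0.6279 − 0.5)/0.07625 = 1.677, below 1.96.
- r = 28: (0.6512 − 0.5)/0.07625 = 1.982, above 1.96.

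So the design rejects at 28. Exact binomial: P(X ≥ 28 | 0.5) = 0.0330 and P(X ≥ 28 | 0.7) = 0.8081. Both match 3.2, and the power matches the 80.8% in 8.3.

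**2. The observed-share rule.** 21/43 = 48.8% and 22/43 = 51.2%, so it passes at 22. P(X ≥ 22 | 0.5) = 0.500 and P(X ≥ 22 | 0.7) = 0.997.

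**3. The disputed counts, 22 to 27.** The probability is P(X ≥ 22) − P(X ≥ 28):

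| True rate | P(22 to 27 of 43) |
|---|---|
| 0.50 | 0.500 − 0.033 = 0.467 |
| 0.60 | 0.607 |
| 0.65 | 0.415 |
| 0.70 | 0.997 − 0.808 = 0.189 |

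**4. Sensitivity to level and method.** The normal-approximation lower limit is p̂ − z√(p̂(1 − p̂)/43).

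| Rule against 50% | Evidence at the edge | Minimum of 43 | Disputed zone |
|---|---|---|---|
| Z ≥ 1.96 (3.2) | 27: 1.677; 28: 1.982 | 28 | 22–27 |
| 97.5% normal limit (level from 3.1) | 27: 0.483; 28: 0.509 | 28 | 22–27 |
| 95% normal limit (8.1) | 26: 0.482; 27: 0.507 | 27 | 22–26 |
| Exact p, one-sided 0.05 | 27: 0.063; 28: 0.033 | 28 | 22–27 |
| Exact p, one-sided 0.025 | 28: 0.033; 29: 0.0158 | 29 (power 0.708 at 70%) | 22–28 |

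If all 48 are analysed, the share rule passes at 24 and the Z rule at 31, so the zone is 24 to 30.

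**5. The ±20%.** A one-sided interval has a single limit and no ± width. The two-sided 95% half-width at n = 43 would be 1.96√(0.25/43) = 14.9 points at p = 0.5, or 1.96√(0.21/43) = 13.7 points at p = 0.7. A half-width of 20 points corresponds to 1.96² × 0.25/0.04 ≈ 24 patients at p = 0.5, or 1.96² × 0.21/0.04 ≈ 20 at p = 0.7. The only 20% in the sizing is 0.70 − 0.50.

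**6. A difference that does not matter.** The success sentence omits the condition that final AHI be under 20. With baseline AHI of at most 30, halving it gives at most 15, so the counts are unaffected.

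**The case against.** The best defence is that the success sentence only sets a benchmark. It ends by naming the PG; the same section says the aim will be tested with a one-sided interval; 3.1.1 describes a comparison with a performance goal; and 3.1.3, 3.2 and 8.1 are all inferential. On that reading the 50% false-success probability arises only if the sponsor disregards the rest of the plan. This is a fair account of the probable intent. It does not remove the problem, because the sentence is worded as a definition of success and nothing subordinates it to the test.

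Stronger readings are tempting but not supported:

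- A reader might infer from the two-directional wording in 8.1 that a rate well below 50% could count as success. Direction is fixed by the one-sided interval in 3.1, the alternative in 3.1.3, the one-sided test in 3.2, and the one-sided interval in 8.1 itself.
- A reader might infer that the lower limit must exceed 70%, from the 20%-beyond-PG language, or only 30%, from the ±20%. No section sets either bar; the test is against 50%, and 70% is the planning alternative.
- A reader might infer that a failed test would be reported as no improvement at all. The formula beside that phrase in 3.1.3 shows that the null is a proportion at or below PG. The words are loose, but the hypothesis is clear.

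**Conclusion.** The point holds as a conflict over which rule decides primary success. For 43 analysed patients, treated as independent with a common response probability, the share rule and the sized test disagree on 22 to 27 responders. That outcome has probability 0.47 at a true rate of 50%, 0.61 at 60% and 0.19 at the planned 70%. The upper edge is not unique: it is 26 under the 95% normal limit in 8.1 and 28 under an exact one-sided 0.025 test. The unreconciled level and method therefore belong to the same problem.

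The ±20% phrase is a mislabelled planning difference. The sample size is not in question: 43 reproduces exactly for the Z test as specified.

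**What to change.** 1. **Section 3.1.** Replace the success sentence with: *The study succeeds only if H0 (responder proportion 50% or less) is rejected in favour of a proportion above 50%.* Delete the ±20% margin of error.
2. **Sections 3.1, 3.2 and 8.1.** Name one level and one method, used identically, and state the resulting minimum count.
   - To keep the sized design: one-sided Z of at least 1.96, 28 of 43, with exact alpha 0.033 stated openly.
   - If the exact binomial p-value at one-sided 0.025 is preferred: 29 of 43, with power restated as 0.708 at a 70% rate.
   - Give the count for other analysed numbers too; for 48 these are 31 (Z rule) and 32 (exact, p = 0.0147).
3. **Section 3.2.** Align H0 and H1 with 3.1.3 and remove the line on P1 minus P0. Keep 70% as the planning value.
4. **Section 8.1.** Write *greater than 50%* for the test, and *powered assuming a 70% responder rate* in place of the sentence about 20% beyond the PG.
5. **Section 3.1.3.** Word the null as *responder proportion is 50% or less*.

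The cost is wording only if the sized Z rule is kept. The exact option also means accepting lower power or revisiting the sample size. Either choice should be made before outcome data are seen.
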